10.2.2 Impact of COVID-19 on adverse events

In order to assess the impact of the COVID-19 global pandemic on the primary safety endpoint of incidence of TEADEs and serious TEADEs, additional summaries will be presented. Summaries of TEADEs and Serious TEADEs will be presented by COVID-19 enrollment period and timing of the ADE relative to the WHO declared COVID-19 pandemic (enrolled prior to pandemic – ADE prior to pandemic, enrolled prior to pandemic – ADE during pandemic, enrolled during pandemic – ADE during pandemic), as defined in Section 4.9.1. ADEs leading to discontinuation will be presented by COVID-19 enrollment period and timing of ADE relative to the pandemic period as well.

For reporting purposes, AEs will be assigned to ‘Prior to COVID-19 pandemic’ or ‘During the COVID-19 pandemic’ based on the following:

- If the date of AE or ADE onset (based on imputed start date) is prior to 11 March 2020 the AE/ADE will be assigned as ‘Prior to COVID-19 pandemic’
- If the date of AE or ADE onset (based on imputed start date) is on or after 11 March 2020 the AE/ADE will be assigned as ‘During the COVID-19 pandemic’

A ‘Post the COVID-19 pandemic’ phase will not be assigned for AE reporting as the pandemic is expected to be ongoing at the time of last subject last visit.

10.2.3 Injection site reaction

Injection site reactions are recorded on the AE CRF page at the time when they occur. All AEs will be coded and classified by system organ class, high level term, and preferred term. An AE with High Level Terms of “Administration site reactions NEC” and “Injection site reactions” will be evaluated as injection site reaction.

All injection site reactions for self-injection with a start date on or following the first self-administration of study treatment through the final self-administration of study treatment + 7 days will be listed.

10.3 Clinical laboratory evaluations

All clinical laboratory evaluations including hematology, chemistry and urinalysis will be collected in PA0012.

10.4 Vital signs, physical findings, and other observations related to safety

Electronic case report form (eCRF) data of vital signs, electrocardiograms, physical examination and pregnancy test results will be collected in PA0012.

11 OTHER ANALYSES

This section contains a detailed description of the analysis of the primary, secondary and other outcome variables. All statistical analyses will be descriptive in nature. No inferential statistical analyses are planned. The analysis is done on FAS-s and FAS-a, respectively.

11.1 Primary outcome variable

The primary outcome variable is the percentage of all subjects able to self-administer safe and effective injections using the given device at DV0004 Week 4. Safe and effective self-injection will be evaluated by the study personnel as defined below:

- Complete dose delivery: Subject self-injects the complete dose of bimekizumab as confirmed by a visual inspection of the bimekizumab-SS-1mL or the bimekizumab-AI-1mL which shows that the IMP is delivered completely (i.e., the container is empty), and
- No ADEs that would preclude continued use of the device presentations for self-injection (i.e., no SADEs and/or ADEs leading to withdrawal from the DV0004 substudy).

All data to assess the primary outcome is collected on the subject self-injection of bimekizumab CRF page for DV0004 Week 4. For the number of subjects with safe and effective self-injections simply the cases which indicated “yes” for the question “Did the subject self-inject the complete dose of Bimekizumab” and “no” for the question “Were there any AEs related to use of the investigational device for self-injection” at DV0004 Week 4 are counted.

The number and percentage of subjects with safe and effective self-injections will be tabulated separately for each device presentation using the relevant FAS population (FAS-s or FAS-a). The 90% CIs based on the Exact Binomial method will be reported as well. The number and percentage of subjects with safe and effective self-injections is tabulated for each device presentation by COVID-19 enrollment period, as described in Section 4.9.1.

Assessments where the self-injection was not performed by the subject will not be included in any summary statistics.

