- No adverse device effects (ADEs) that would preclude continued use of the device presentation for self-injection (ie, no serious adverse device effects [SADEs] and/or ADEs leading to withdrawal from the DV0004 substudy)

The secondary study objectives and other study objectives are provided in Section 3.2 and Section 3.3, respectively. Of note, one of the other study objectives is to assess trough PK levels associated with self-injection using the test device presentation, injection by study personnel using the 1mL PFS, injection site (abdomen or thigh), and BMI category (by tertile). The secondary outcome variable, other outcome variables, and the other safety variable are listed in Section 4.1.2, Section 4.1.3, and Section 4.1.3.4, respectively.

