4 STUDY VARIABLES

4.1 Outcome variables

4.1.1 Primary outcome variable

The primary outcome variable is the ability to self-administer safe and effective injections using the bimekizumab-SS-1mL or the bimekizumab-AI-1mL at Week 4. Safe and effective self-injection will be evaluated by the study personnel and is defined as:

- Complete dose delivery. Subject self-injects the complete dose of bimekizumab as confirmed by a visual inspection of the bimekizumab-SS-1mL or the bimekizumab-AI-1mL which shows that the IMP is delivered completely (ie, container is empty), and
- No ADEs that would preclude continued use of the device presentations for self-injection (ie, no S.ADEs and/or ADEs leading to withdrawal from the DV0004 substudy).

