14.3.1 Analysis of the primary outcome variable

The primary outcome variable is the percentage of all subjects able to self-administer safe and effective injections using the given device presentation at Week 4. Safe and effective self-injection will be evaluated by the study personnel as defined in Section 4.1.1.

The number and percentage of subjects with safe and effective self-injections will be tabulated separately for each device presentation overall using the relevant FAS population (FAS-s or FAS-a). The 90% CIs based on the Exact Binomial method will be reported as well.

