2.2 Study variables

2.2.1 Outcome variables

2.2.1.1 Primary outcome variable

The primary outcome variable is the ability to self-administer safe and effective injections using the bimekizumab-SS-1mL or the bimekizumab-AI-1mL at Week 4.

Safe and effective self-injection will be evaluated by the study personnel and is defined as:

- Complete dose delivery: Subject self-injects the complete dose of bimekizumab as confirmed by a visual inspection of the bimekizumab-SS-1mL or the bimekizumab-AI-1mL, which shows that the investigational medicinal product (IMP) is delivered completely (i.e., container is empty), and
- No adverse device events (ADEs) that would preclude continued use of the device for self-injection (i.e., no serious adverse device events [SADEs] and/or ADEs leading to withdrawal from the DV0004 substudy).

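### SAP 11.1 counts any device-related AE as a failure of the primary outcome, although the outcome is defined by serious or withdrawal-causing ADEs only; the change is not declared and carries over to SAP 11.2

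*SAP*

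**What the plan says.** The definition is consistent across both documents. Protocol 4.1.1 asks for complete dose delivery and "No ADEs that would preclude continued use of the device presentations for self-injection". The Summary (protocol 1) spells this out as "no serious adverse device effects [SADEs] and/or ADEs leading to withdrawal from the DV0004 substudy", SAP 2.2.1.1 as "no serious adverse device events [SADEs] and/or ADEs leading to withdrawal from the DV0004 substudy", and the bullets of SAP 11.1 as "no SADEs and/or ADEs leading to withdrawal from the DV0004 substudy". Protocol 14.3.1 ties the planned analysis to it: "Safe and effective self-injection will be evaluated by the study personnel as defined in Section 4.1.1".

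The paragraph after the bullets in SAP 11.1 says how the outcome is computed. The source is one page: "All data to assess the primary outcome is collected on the subject self-injection of bimekizumab CRF page for DV0004 Week 4". The rule begins "For the number of subjects with safe and effective self-injections simply the cases which indicated". It goes on to require a *yes* on complete dose and a *no* to "Were there any AEs related to use of the investigational device for self-injection".

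SAP 11.2 analyses the Baseline (secondary) outcome in the same manner, from the Baseline injection page. SAP 3.8 lists four changes to protocol-defined analyses. Only the third mentions the primary outcome, and it concerns keeping subjects with deviations in the FAS. SAP 3.8.1 lists the primary outcome only for COVID-19 summaries. None of the four SAP amendment logs describes a changed success rule.

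**The concern.** The CRF question as printed has no qualifier for seriousness or withdrawal. Protocol 11.1.1.1 and SAP 10.2.1 treat any AE related to use of the device as an ADE. SAP 10.2.1 tabulates serious TEADEs and TEADEs leading to discontinuation separately from all TEADEs. The plan itself therefore treats the events that define failure as a subset of what the question captures.

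The study is estimation only, so the percentage and its exact 90% CI for each device are the primary result. A programmer who follows the counting sentence produces a percentage for a stricter outcome than the one defined. A programmer who follows the bullets produces the defined one. The same data can thus give two primary results, and the plan does not say that the two differ.

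**Working it through.** The plan states no figure for this outcome, so there is nothing to reproduce first. The check has two parts.

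**1. Classification.** All subjects below delivered the complete dose at Week 4.

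| Device-related AE | By definition | By counting sentence |
|---|---|---|
| None | success | success |
| Non-serious, subject stays in DV0004, marked on the injection page | success | **failure** |
| Serious or led to withdrawal, marked on the injection page | failure | failure |

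The second row is the conflict. It follows from the wording alone.

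**2. Size.** Inputs:

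- n: subjects with an observed Week 4 assessment. About 100 per device are planned (SAP 2.3.6). SAP 3.1 bases percentages on observed data, so n may be lower.
- k: subjects in the second row. This is assumed, because neither document gives an ADE rate.
- f: true failures under the definition, also assumed.
- Interval: 90% exact binomial (SAP 11.1).

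Defined rate = (n - f)/n and counted rate = (n - f - k)/n, so the shift is -100 × k/n points. Per subject this is 100/100 = 1.00 point at n = 100, 100/90 = 1.11 at n = 90 and 100/80 = 1.25 at n = 80.

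For x successes, the lower limit is the 5% quantile of Beta(x, n - x + 1) and the upper limit is the 95% quantile of Beta(x + 1, n - x). At x = n the lower limit reduces to 0.05^(1/n), and 0.05^(1/100) = 0.9705.

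| n = 100 | Defined (90% CI) | Counted, k = 1 | Counted, k = 5 |
|---|---|---|---|
| f = 0 | 100% (97.05-100) | 99.0% (95.34-99.95) | 95.0% (89.77-98.01) |
| f = 1 | 99.0% (95.34-99.95) | 98.0% (93.84-99.64) | 94.0% (88.50-97.36) |

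With k = 0 the two rules agree.

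**Secondary point: one page as the source.** SAP 10.2.1 says AEs are entered on the AE page when they occur, and protocol 11.1.2.3 collects ADEs up to the follow-up call. The counting sentence does not read the AE page. A qualifying event that starts after the injection page is completed could be missed unless the page is updated. Week 4 is the last DV0004 injection and only the Week 5 call follows, so this would mainly be a late-onset SADE. Whether it happens depends on the eCRF (v6.0, cited in SAP 1), which is not among the documents.

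**The case against.** - **The CRF question may be abbreviated, or may have follow-up items on seriousness or withdrawal.** This cannot be excluded without the eCRF. The SAP sentence uses no such item, however, so anyone following it would ignore one.
- **The rule is conservative and is printed directly under the definition.** The any-AE wording can indeed only lower the success rate. It is still a different outcome from the protocol's, and a change to a protocol-defined analysis belongs in SAP 3.8.
- **The analysis is descriptive.** This stands: no hypothesis test, power or threshold is affected.
- **The events will be visible anyway.** This stands in part. Protocol 14.2, SAP 3.1 and SAP 10.2.1 promise full listings, including all ADE data, and these may allow the defined outcome to be rebuilt subject by subject. The tabulated primary percentage would still not be the defined one.
- **The single-page source may do no harm.** Largely fair. Protocol 13.3.1 and 13.3.2 allow corrections and require discrepancy checks. The outcome is ability at Week 4, judged by study personnel. The window to the last self-injection plus 7 days belongs to the TEADE definition in SAP 10.2.1, not to this outcome. A reader might infer that the page rule inflates the success rate. The documents do not establish that, so the matter is a request for clarification.

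**Conclusion.** The point holds as a conflict of wording inside SAP 11.1. The counting sentence, followed as written, does not compute the outcome that the same section, SAP 2.2.1.1 and the protocol define. The departure is undeclared and reaches the Baseline outcome through SAP 11.2.

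Confidence is high on the wording and low on the numerical effect. Everything beyond the per-subject shift rests on assumed counts, and the effect is zero if every device-related AE marked on the page is serious or leads to withdrawal, or if there is none.

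Two stronger readings are not supported. A reader might infer that the reported rates will be materially wrong or biased in a known net direction. The any-AE wording pushes them down, but its size is unknown, and any upward effect of the page-only source is unproven. A reader might also attribute to this rule the loss of subjects who withdraw after a Baseline ADE and so have no Week 4 assessment. That follows from the observed-data denominator in SAP 3.1. It is a separate matter, which correcting the counting sentence would not alter.

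**What to change.** Replace the counting sentence in SAP 11.1, and so in 11.2. Success is a *yes* to complete dose and no device-related AE associated with that injection that is serious or led to withdrawal from DV0004. Use the seriousness and withdrawal fields in the AE data already collected.

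State how an event is linked to an injection and what period is covered. Protocol 11.1.2.1 describes recording the device relationship and the device presentation, but no link to a particular injection. If onset dates are used, say how partially dated events are assigned. SAP 4.2 moves some incomplete start dates to the first dose, which could place a Week 4 event at Baseline.

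Report complete dose with no device-related AE of any kind as a supportive line. Alternatively, if the any-AE rule is meant to be primary, declare it in SAP 3.8 and report both percentages.

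The cost is a short text change with its linkage rule, a small derivation, and reconciliation of injection-page and AE-page entries before lock. Two checks against the eCRF are needed: whether the injection page is updated after the visit, and whether discontinuation in the AE data means withdrawal from DV0004. No new data collection is expected, subject to those checks.

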6.3 Withdrawal criteria

Since DV0004 is a substudy of PA0012, all DV0004 withdrawal criteria are captured in the PA0012 protocol. There are no additional DV0004-specific withdrawal criteria beyond those that are described in PA0012. Subjects are free to withdraw from DV0004 at any time, without prejudice to their continued care. Subjects who withdraw from DV0004 but remain eligible for PA0012 (ie, subjects who have a medical condition or personal preference that precludes further self-injection) may continue in PA0012. These subjects must perform an SFU telephone call 1 week after their last self-injection in DV0004.

Subjects who are withdrawn from bimekizumab treatment during DV0004 will also be required to follow the PA0012 withdrawal procedures.

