7 MEASUREMENTS OF TREATMENT COMPLIANCE

During the Treatment Period of this study, IMP administration (either self-administration or study personnel-administration) will be performed in the clinic and observed by the Investigator or his/her designee; monitoring subject compliance is therefore not applicable.

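### SAP 11.1 removes every Week 4 injection not performed by the subject, so an attending subject who could not or would not self-inject leaves the primary percentage instead of counting as not successful

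*SAP*

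**What the plan says.** Protocol 4.1.1 has two conditions for success. The first is complete dose delivery: "Subject self-injects the complete dose of bimekizumab as confirmed by a visual inspection". The second is the absence of serious adverse device effects and of "ADEs leading to withdrawal from the DV0004 substudy". Protocol 14.3.1 defines the primary variable as "the percentage of all subjects able to self-administer safe and effective injections" with the given device at Week 4, tabulated on the device-specific FAS with an exact 90% CI.

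SAP 11.1 repeats this definition and makes it operational. It states: "All data to assess the primary outcome is collected on the subject self-injection of bimekizumab CRF page for DV0004 Week 4". A success is a yes to "Did the subject self-inject the complete dose of Bimekizumab" together with a no to the question on device-related adverse events. The section then closes with: "Assessments where the self-injection was not performed by the subject will not be included in any summary statistics". The same sentence stands in SAP 11.2 and SAP 11.3.

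Four other places bear on the point:

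- SAP 3.4.3 admits a subject to the FAS on one self-injected dose with an assessment. Baseline is enough.
- SAP 7 says that "IMP administration (either self-administration or study personnel-administration) will be performed in the clinic", where Protocol 7.7 mentions self-administration only. SAP 9.1 plans for Week 4 and Week 8 PK samples whose preceding injection was given by site personnel or a caregiver.
- SAP 3.1 takes the analysis set as the default denominator, but limits outcome percentages to subjects with observed data unless otherwise specified.
- SAP 3.8 lists four numbered changes to the protocol-defined analyses. This exclusion is not among them.

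**The concern.** The endpoint asks whether subjects can still self-inject four weeks after training. A subject who attends Week 4 and needs someone else to inject, because of inability, refusal or a malfunctioning device, has not met the definition of success. The closing sentence of SAP 11.1 does not count that subject as not successful. It deletes the record. For these subjects the estimate changes from ability among all FAS subjects to success among those who performed the injection.

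The study is descriptive, with no test and no threshold, so this percentage and its interval are the whole primary result. A rule that can move it in one direction only, and that is not declared as a departure from the protocol, deserves correction.

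**Working it through.** **Who is affected.** The subject is in the FAS through the Baseline self-injection (SAP 3.4.3). At Week 4 someone else injects. Under Protocol 4.1.1 the first condition for success fails, because the subject did not self-inject. Under the last sentence of SAP 11.1 the assessment is left out of the summary. Attempted but incomplete self-injections are not affected: the subject performed them, so they stay in and count as not successful.

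**Inputs.** There is no precision figure in the plan to reproduce; the sample size is practical (200/2 = 100 per arm, Protocol 14.10 and SAP 2.4). The interval is exact binomial, 90% (SAP 11.1). The following are assumptions, because the documents give no counts:

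- N = 100 FAS subjects in an arm
- k = subjects injected by someone else at Week 4 because of inability, refusal or malfunction
- f = other failures
- u = subjects with a documented unrelated reason, left out of both calculations

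**Formulas.** With s = N − k − f − u successes:

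- SAP 11.1 rule: s/(N − k − u)
- Counted as not successful: s/(N − u)
- Difference: [s/(N − k − u)] × k/(N − u), which is never negative

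The exact 90% limits for x of n are the 5% quantile of Beta(x, n − x + 1) and the 95% quantile of Beta(x + 1, n − x). When x = n the lower limit is 0.05^(1/n); for n = 98 this is 0.970.

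| k | f | u | SAP 11.1 rule (90% CI) | Counted as not successful (90% CI) | Rise, points |
|---|---|---|---|---|---|
| 0 | 0 | 0 | 100/100 = 100% (97.0–100) | 100/100 = 100% (97.0–100) | 0 |
| 1 | 0 | 0 | 99/99 = 100% (97.0–100) | 99/100 = 99.0% (95.3–99.9) | 1.00 |
| 2 | 0 | 0 | 98/98 = 100% (97.0–100) | 98/100 = 98.0% (93.8–99.6) | 2.00 |
| 5 | 0 | 0 | 95/95 = 100% (96.9–100) | 95/100 = 95.0% (89.8–98.0) | 5.00 |
| 2 | 3 | 0 | 95/98 = 96.9% (92.3–99.2) | 95/100 = 95.0% (89.8–98.0) | 1.94 |
| 2 | 3 | 2 | 93/96 = 96.9% (92.1–99.1) | 93/98 = 94.9% (89.6–98.0) | 1.98 |

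Over k = 1 to 5, f = 0 to 5 and u = 0 to 2, the rise is 0.95 to 1.02 points per affected subject. With no other failures the SAP rule reports 100% whatever k is. The lower confidence limit rises too, because the same s is set against a smaller n.

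**Secondary variable.** The sentence in SAP 11.2 has a narrower reach. A subject who did not self-inject at Baseline is in the FAS only through a later self-injection at Week 4.

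**The case against.** The case for leaving the text alone has several parts.

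- **Withdrawals.** A reader might infer that the sentence also removes the group in Protocol 6.3, "subjects who have a medical condition or personal preference that precludes further self-injection". The documents do not support that. Those subjects withdraw from DV0004. If they leave before Week 4 they have no Week 4 assessment for the sentence to exclude. Their denominator depends on SAP 3.1, where the observed-data rule points to dropping them, and the analysis-set default, with the reference to all subjects in SAP 11.1, points to keeping them. That is a separate ambiguity, and Protocol 6.3 is not evidence on this sentence.
- **The CRF.** It is tempting to say that the SAP's own count would score these subjects as failures, because the complete-dose question would be answered no. That is the natural answer, but the form is not available, and the page may be left blank when someone else injects. The conflict with the definition in Protocol 4.1.1 does not depend on this step; confidence does.
- **Refusal.** The objective speaks of ability, so treating refusal as not successful is a choice that must be declared. Cases of inability and malfunction are removed all the same.
- **Frequency.** Entry requires willingness and the investigator's judgement that the subject can use the device (Protocol 6.1), FAS members have self-injected at least once, and the protocol describes no route for someone else to inject in DV0004. The number may well be zero. But SAP 7 and SAP 9.1 foresee such injections, and the exclusion would have no purpose otherwise.
- **Transparency.** SAP 3.1 displays the denominator and the data are listed. A smaller denominator does not tell the reader that the missing subjects were unable or unwilling.
- **No imputation.** Protocol 14.2 rules imputation out. A known inability or refusal is an observed outcome, so counting it imputes nothing. An unrecorded reason is different, and scoring it as a failure in the headline alone would go too far.

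**Conclusion.** The point holds for FAS subjects who attend Week 4 and are injected by someone else because of inability, refusal or device malfunction. For them SAP 11.1 departs from the protocol's primary variable, without a declaration in SAP 3.8, and in a direction that can only raise the estimate relative to counting them as not successful. The size is about 1 percentage point per subject, on the assumption of 100 FAS subjects per arm; the number of such subjects is unknown and may be zero.

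It does not follow that the reported percentage will be materially too high, that every injection given by someone else is a failure (a logistical reason says nothing about ability), or that withdrawals before Week 4 are mishandled by this sentence. No test, power or threshold is affected. Confidence is medium, because completion of the CRF page when someone else injects cannot be checked.

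**What to change.** In SAP 11.1, delete the blanket exclusion for the primary variable and put a rule by reason in its place:

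- Count as not successful those FAS subjects whose Week 4 injection was not self-performed because of inability, refusal or device malfunction.
- Leave out only those with a documented reason unrelated to the device or to ability or willingness, and show their number in the table.
- Show subjects with an unrecorded reason in a separate row, and report the percentage twice: with them left out and with them counted as not successful.
- Report the percentage under the current rule as a sensitivity line.
- State which SAP 3.1 denominator applies to FAS subjects withdrawn before Week 4.

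Apply the same rule in SAP 11.2, with the FAS definition unchanged. In SAP 11.3, keep the exclusion for the pain scale and the SIAQ, but not for structural and functional integrity (11.3.4 and 11.3.5), so that malfunctioning devices are not dropped from those tables. List all of this in SAP 3.8.

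The cost is SAP wording, a few table rows and a sensitivity line. Who injected must already be known to apply the current rule, discontinuation reasons are already reported (SAP 5.1), and pandemic-related missed visits are already recorded (SAP 5.3). The documents describe no CRF item for why an attending subject did not self-inject, so some reasons may need a query. The headline percentage may be slightly lower.
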